12.5.2 VR READY study team Responsibilities

Following the initial report, all SAEs should be followed up to resolution wherever possible, and further information may be requested by the VR READY study team. For follow-up information, sites to update the initial copy of the SAE form and put a single line through the old information and new information added.

The VR READY study team should continue reporting SAEs until the participant receives the last part of the intervention.

Once an SAE is received by the VR READY study team, it will be evaluated by the VR READY study team and sent to the CI (or their delegate) for an assessment of expectedness.

For all non-CTIMP studies, including clinical investigations of medical devices, only reports of related and unexpected SAEs should be submitted to the REC. These should be sent within 15 days of the CI becoming aware of the event. Reports of related and unexpected SAEs in double-blind trials should be unblinded. There is no requirement for Annual Safety Reports (ASRs) in addition to the information provided through the annual progress report.

12.6 Procedure following disclosure of psychological distress

If any participant answers that they are severely or extremely anxious or depressed on the EQ5D, has a raw score of 13 or more on the DASS-10 or a score of more than 0 on DASS-10 item 12 for suicidal thoughts, this should be flagged to the clinical CI and the Critical Care clinical psychologist (contact details below).

Contact Critical Care Clinical Psychologist: Details to be added

If no one is available from the Psychology team, the Crisis team: can be contacted on:

Royal Glamorgan - [name]

Prince Charles - [name]

13 Statistical considerations

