9.3 Recruitment rates

We will aim to recruit up to 25 participants from ICU at an expected rate of 3.5-4 per month. Family member/ loved ones will be additional to that target sample and we do not expect to include more than 15 family members/ loved ones.

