11.3 Phase 3 - Feasibility Study

Following the development of the VR intervention, its use will be piloted in a small, one arm feasibility study. Up to 25 participants will be recruited to receive the intervention for 2 weeks in the in-patient setting. If participants are discharged prior to completion of the 2-week intervention delivery, they will be able to take the headset home with them.

Following the provision of consent, participants will complete the baseline assessments. We anticipate that for the majority of participants, they will be unable to complete self-report items independently. Therefore, a member of the research team will aid completion by reading out questions and confirming the participants response, which will be entered directly into REDCap using a tablet or laptop.

Where participants are required to complete follow-up assessments at home, they will be asked for their preferred method for completion (either on paper, electronically or research team assisted via the telephone) and guidance for how to complete the assessments will be provided.

The participant will be provided with a VR headset and instructed on how to use the equipment and how to engage with the intervention. A written instruction manual will also be provided. For at least the first two days of the intervention, the participant will be assisted by a member of the research team to guide use of the VR apparatus, troubleshoot any problems with use and ensure that the participant isn't experiencing any undue problems from using the headset. Beyond this, if the participant continues to struggle with using the apparatus independently (i.e. through muscle weakness) then a member of the research team will be available daily to assist. Participants in the inpatient setting will be assessed for any current episodes of delirium prior to using the headset using the CAM-ICU. If a participant progresses to independent use of the VR headset, formal delirium assessments will not be performed as it would be expected that any bout of delirium would preclude independent usage, but research staff will continue to check in with participants regularly.

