- iii) Forest This features a computer generated forest scene with accompanying soundscape where the user is guided through a breathing exercise "Relax and practice your breathing in a relaxing forest environment"

Information

- i) Meet the psychologist a consultant psychologist visits the patient in a hospital environment to explain their role and why the patient might interact with them.
- ii) Meet the occupational therapist an occupational therapist visits the patient in a hospital environment to explain their role and why the patient might interact with them.
- iii) Meet the dietician a dietician visits the patient in a hospital environment to explain their role and why the patient might interact with them.
- iv) Meet the speech and language therapist a speech and language therapist visits the patient in a hospital environment to explain their role and why the patient might interact with them.
- v) Meet the physiotherapist- a physiotherapist visits the patient in a hospital environment to explain their role and why the patient might interact with them.

Following the end of the intervention delivery period, participants will be asked to perform follow-up assessments at conclusion on intervention delivery at 2wks and 4wks follow-up. If the participant remains an inpatient, participants will be assessed within their current hospital setting. For participants that have been discharged, they will be contacted to complete the follow-up assessments. This will either be by post (for preferred paper completion), by email (for preferred electronic completion) or by telephone.

Once follow-up assessments have been completed, the participant will be contacted to arrange an appointment for a qualitative interview. This will take place approximately 1 month following completion of the follow-up assessments. This may take place either in person at a location determined by the participant, or via secure video conferencing software such as Zoom or Microsoft teams. If the participant chooses to conduct the interview remotely, and has taken the VR equipment home with them at discharge, a separate arrangement will be made for the research team to either collect the DR.VR equipment or have the participant return it.

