		achievement and			
		progress; enjoyment			
		and pleasure			
Brief resilience	Psychological	This consists of 6 items	5 mins	Baseline	ICU
Scale	resilience	relating to response or		only	patients
		coping to adverse life		J,	and
		events. Participants			family
		are asked to rate each			members
Richards Campbell	Sleep	This is a 6 item	5 mins	Baseline	ICU
Sleep	эгсер	questionnaire	3 1111113	and	Patients
Questionnaire		designed to address		Follow	only
Questionnane		sleep and sleep		Up	Omy
		·		Op	
		i dilality Participants			1
		quality. Participants			
		are asked to respond			
		are asked to respond to questions on a scale			
		are asked to respond to questions on a scale of 0-100. Questions			
		are asked to respond to questions on a scale of 0-100. Questions cover; sleep depth,			
		are asked to respond to questions on a scale of 0-100. Questions cover; sleep depth, latency, awakenings,			
		are asked to respond to questions on a scale of 0-100. Questions cover; sleep depth, latency, awakenings, ability to return to			
		are asked to respond to questions on a scale of 0-100. Questions cover; sleep depth, latency, awakenings, ability to return to sleep, sleep quality,			
		are asked to respond to questions on a scale of 0-100. Questions cover; sleep depth, latency, awakenings, ability to return to sleep, sleep quality, with an optional item			
		are asked to respond to questions on a scale of 0-100. Questions cover; sleep depth, latency, awakenings, ability to return to sleep, sleep quality, with an optional item concerning noise.			
DASS-10	Depression and	are asked to respond to questions on a scale of 0-100. Questions cover; sleep depth, latency, awakenings, ability to return to sleep, sleep quality, with an optional item concerning noise. This questionnaire	7 mins	Baseline	ICU
DASS-10	Depression and Anxiety	are asked to respond to questions on a scale of 0-100. Questions cover; sleep depth, latency, awakenings, ability to return to sleep, sleep quality, with an optional item concerning noise. This questionnaire consists of 10 items.	7 mins	and	patients
DASS-10	· •	are asked to respond to questions on a scale of 0-100. Questions cover; sleep depth, latency, awakenings, ability to return to sleep, sleep quality, with an optional item concerning noise. This questionnaire consists of 10 items. Respondents are	7 mins	and Follow	patients and

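### The suicidal-thoughts trigger in section 12.6 points to item 12 of a questionnaire that section 11.3.1 says has 10 items

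*Protocol*

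**What the plan says.** Section 12.6 sets out when a participant's answers must be escalated for psychological distress. There are three alternative triggers, and any one is enough:

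- an answer of "severely or extremely anxious or depressed on the EQ5D";
- a participant who "has a raw score of 13 or more on the DASS-10";
- "a score of more than 0 on DASS-10 item 12 for suicidal thoughts".

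The action is the same for each: "this should be flagged to the clinical CI and the Critical Care clinical psychologist".

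The outcome table in section 11.3.1 lists the DASS-10 as a measure of depression and anxiety, given to ICU patients and family members at baseline and follow-up. It describes the form in these words: "This questionnaire consists of 10 items". The protocol does not list the items, give their scoring, or say which of them concerns suicidal thoughts.

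**The concern.** An item numbered 12 cannot be found by counting on a form with 10 items. The two statements may disagree because the item number is wrong, because the form is longer than described, or because the number follows a scheme the protocol does not mention. The reader cannot tell which.

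This matters because the number sits in an operative safety rule. Of the three triggers, the item trigger is the only one that responds to suicidal thoughts when the participant's total is below 13 and the EQ-5D answer is less than severe. If the reference is wrong, finding that person depends on someone recognising the item by its wording. The mismatch also raises a second question: if a longer form is in use, does the cut-off of 13 belong to that form?

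**Working it through.** **1. Item number against item count.**

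| Statement | Section | Value |
|---|---|---|
| Item that triggers the flag | 12.6 | 12 |
| Items in the DASS-10 | 11.3.1 | 10 |

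12 > 10, so the cited number lies 2 beyond the last item. Both statements are current text, not amendment history. The DASS-10 row appears twice in the extracted table, and both copies give 10 items. No section mentions appended items, numbering carried over from a parent scale, or a separate suicidality question.

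**2. Do the other triggers still work?** The EQ-5D trigger does not depend on the DASS-10. For the total score, the item scoring is not stated, so I assume a maximum of 3 per item and show 2 and 4 as a range. The maximum total is ten times the item maximum:

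- item maximum 2: 10 × 2 = 20
- item maximum 3: 10 × 3 = 30
- item maximum 4: 10 × 4 = 40

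A total of 13 can be reached in each case, so this trigger works on the 10-item form described.

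**3. Would the total score catch the same person?** The item trigger fires at any score above 0. The points still needed from the other nine items to reach 13 are 13 minus the score on the item:

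| Score on the suicidal-thoughts item | Points still needed |
|---|---|
| 1 (lowest score that fires the trigger) | 13 − 1 = 12 |
| 2 (maximum if scored 0–2) | 13 − 2 = 11 |
| 3 (maximum if scored 0–3) | 13 − 3 = 10 |
| 4 (maximum if scored 0–4) | 13 − 4 = 9 |

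Even the strongest possible answer on that item leaves 9 to 11 points to come from elsewhere. A participant who falls short of that, and who does not give a severe or extreme EQ-5D answer, is flagged by the item trigger alone.

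**4. How many forms does the rule cover?**

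- Patients: up to 25 (section 9.3).
- Relatives: "we do not expect to include more than 15 family members/ loved ones" (section 9.3).
- Total: 25 + 15 = 40.
- Occasions: Table 2 marks outcome measures at baseline and week 2, which is 2. Section 11.3 says "participants will be asked to perform follow-up assessments at conclusion on intervention delivery at 2wks and 4wks follow-up", which with baseline makes 3.
- Forms: 40 × 2 = 80, or 40 × 3 = 120.

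These figures measure exposure to the rule. They do not estimate missed disclosures.

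**The case against.** The strongest reply is that the clause names its item by content as well as by number. If the form has a question on suicidal thoughts, a member of staff will know which answer is meant, and the number is only a labelling slip. This stands as far as it goes, but the protocol does not show that the form has such a question, so the safeguard cannot be confirmed from the text.

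A second reply is that the number may follow the case report form or a parent scale, with ten items still present. The documents neither say nor exclude this. If it is so, the protocol needs to say it, because a reader of section 11.3.1 would count from 1 to 10.

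A third reply is that staff often see the answers. For most participants at baseline, "a member of the research team will aid completion by reading out questions and confirming the participants response". At follow-up, inpatients are assessed in hospital, telephone help is available, and a researcher checks and enters returned paper forms (sections 11.3, 11.3.1 and 15.2.1). This lowers the risk. It does not remove it: the paper checks described are for missing, illegible or unusual values and consistency, not for distress triggers, and section 15.2.2 allows remote electronic completion through a personal link.

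Finally, the counts are upper-end figures. Fifteen relatives is an expectation, section 9.1 lets some relatives take part only as sources of information, and Table 2 supports two occasions rather than three. Two occasions give at most 80 forms on these numbers. None of this changes the mismatch or the correction.

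**Conclusion.** The concern holds. The suicidal-thoughts trigger in section 12.6 is wrong as written when set beside section 11.3.1: it cannot be applied by number to the instrument described. This is certain from the text and needs no assumption. The other two triggers are unaffected.

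The practical consequence is less certain. It depends on whether the form has a suicidal-thoughts item and whether staff recognise it by wording. The gap is confined to participants who report suicidal thoughts, score below 13 in total and give no severe or extreme EQ-5D answer. Their number cannot be derived from the protocol. The 9-to-11-point range rests on the assumed item scoring; the 12-point figure needs only the clause's own threshold and a score of 1.

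The correction should be made: the rule protects people recovering from critical illness and their relatives, and putting it right costs very little.

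**What to change.** Take the DASS-10 form actually administered and confirm that it contains an item on suicidal thoughts. Then:

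- **If it does:** cite that item in section 12.6 by its number on that form and by its wording.
- **If the form has more than 10 items:** also correct the count in section 11.3.1 and confirm that the cut-off of 13 belongs to that form.
- **If the numbering comes from another scale:** state this in both sections.
- **If there is no such item:** the clinical team should decide how suicidal thoughts are to be detected.

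If any forms have already been completed, check them against the corrected rule. The clinical threshold and the response remain with the clinical team. The documents do not support any particular replacement number, so none is proposed here.

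The cost is a wording correction in section 12.6, possibly one in section 11.3.1, and a review of completed forms if any exist. If the form does contain the item, sample size, assessments and schedule do not change.

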13.1 Sample size

This study is focussed on intervention development and the piloting of the resulting intervention in a small number of participants to determine feasibility and acceptability of the intervention. Based on pragmatic reasons for running a focus group, we expect each focus group to contain no more than 8 participants each (16 in total across the two groups). For the feasibility study, no quantitative analysis will be performed. We have selected a sample size of up to 25 participants as a pragmatic target for how many people can be recruited from a single site over the given timeframe and at a level that sufficient data will be generated for our planned analysis.

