5.3 Primary outcomes measure(s)

For the phase 3 study, the primary outcome measure will be feasibility as determined by: recruitment, retention, data completeness and intervention adherence. Each measure of feasibility will be assessed according to the pre-defined criteria outlined below.

Variable		Progression Criteria		
		Red	Amber	Green
	No approached willing to participate	<5%	5-19%	20%

Recruitment	No screened actually recruited	<50%*	50-74%	75-100%
	No. recruited	< 6 in total	6-12	12-25
Retention	No of partially active trial participants at			
	primary end point	<50%	50-79%	80%
Adherence	Completion of intervention sessions*	<50%	50-79%	80%
Data	Completion of baseline measures	<50%	50-79%	80%
Completeness	Completion of follow up measures	<50%	50-69%	70%

^{*}to be refined following intervention development in Phase 1 and Phase 2.

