13.3 Procedures for reporting deviation(s) from the original SAP

There will be no quantitative analysis of the data collected, so no SAP will be generated.

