14.1 Qualitative analysis

Data analysis across all phases will be purely qualitative. Audio recordings of focus groups in phase 1 and participant and HCP/ researcher interviews from the feasibility study will be transcribed verbatim. Transcripts will be subject to analysis using a framework and mapping approach followed

by a thematic analysis informed by Braun & Clarke²³ and Adu²⁴ using NVivo software as a data management tool.

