14.2 Quantitative analysis

In phase 3 of the study, we will ask participants to complete the outcome measures selected through the Phase 1 activities, however, data from the completed outcome measures in phase 3 will not be analysed. Outcome measure data will be collated and summarised in a tabular format for triangulation with the interview data using a mixed methods approach²⁵ to complement their qualitative evaluation.

15 Data Management

This study will consist largely of qualitative data, with some quantitative data being collected in Phase 3, but with no plans for formal statistical analysis.

Source Data is defined as "All information in original records and certified copies of original records of clinical findings, observations or other activities in a clinical study necessary for the reconstruction and evaluation of the study. Source data are contained in source documents." There is only one set of source data at any time for any data element, as defined in site source data agreement.

Study data	Source Data				
	Participan t medical notes	CRF (paper)	CRF (electronic)	Audio file saved on S Drvie	Site file
Consent	Х				Х
Focus group data				Х	
Selected outcome measures		х	х		
Interview data				х	
Withdrawal	Х		х		х

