21.1 Monitoring

The clinical study risk assessment has been used to determine the intensity and focus of central and on-site monitoring activity in the VR-READY study. Due to the low risk nature of the research and the lack of quantitative data collection, there will be no planned monitoring at site. There will be low levels of monitoring in place for qualitative data and study progress. This will be detailed in the monitoring plan.

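### Sections 13.1, 13.3 and 14.1 exclude all quantitative analysis, which contradicts the seven numeric progression criteria that Section 5.3 makes the Phase 3 primary outcome

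*Protocol*

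**What the plan says.** Protocol Section 5.3 states that for Phase 3 "the primary outcome measure will be feasibility as determined by: recruitment, retention, data completeness and intervention adherence", and that "Each measure of feasibility will be assessed according to the pre-defined criteria outlined below". The table that follows gives red, amber and green cut-offs for seven rows: three on recruitment, one on retention, one on adherence and two on data completeness.

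The analysis sections say the opposite:

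- Section 13.1: "For the feasibility study, no quantitative analysis will be performed".
- Section 13.3: "There will be no quantitative analysis of the data collected, so no SAP will be generated".
- Section 14.1: "Data analysis across all phases will be purely qualitative".
- Section 14.2 deals only with the questionnaires. They are not to be analysed, but "Outcome measure data will be collated and summarised in a tabular format for triangulation with the interview data".

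The opening of Section 15 is narrower. It acknowledges some quantitative data in Phase 3 and rules out only formal statistical analysis.

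Section 21.1 gives two reasons for its approach to monitoring: the low risk of the research and the "lack of quantitative data collection, there will be no planned monitoring at site".

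**The concern.** Placing a measure in a red, amber or green band requires a numerator, usually a denominator, and a comparison with a cut-off. That is quantitative analysis, however simple. The protocol requires it in Section 5.3 and excludes it in three other places.

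A protocol can normally leave such detail to the SAP. Section 13.3 closes that route by saying there will be none, so the protocol is the only place where the primary evaluation can be specified.

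What is at stake is how the progression decision is reached. With no stated method, the team must choose denominators and presentation after the data are in, and a reader cannot tell whether those choices were made in advance. The mistaken premise also reaches Section 21.1, where a supposed absence of quantitative data helps to justify the monitoring approach although the primary outcome rests on such data.

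**Working it through.** **Step 1. Are the Section 5.3 criteria quantitative?** The rows are:

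1. those approached who are willing to take part (%)
2. those screened who are recruited (%)
3. number recruited (count)
4. retention (%)
5. adherence (%)
6. completion of baseline measures (%)
7. completion of follow-up measures (%)

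That is six percentages and one count, each with numeric cut-offs.

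**Step 2. Does any analysis section cover them?** Section 13.1 excludes quantitative analysis for the feasibility study as a whole. Section 13.3 excludes it for the data collected. Section 14.1 excludes it for all phases. Section 14.2 covers the questionnaires only. Recruitment, retention, adherence and completeness are named in none of them, and no exemption is made.

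**Step 3. Are the inputs collected?** Yes.

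- Section 9.2 keeps a screening log to inform the feasibility of recruitment.
- Section 11.3.1 has headset usage recorded continuously and downloaded.
- Section 15.2.1 records data queries for use in the feasibility outcomes.

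The gap is therefore in the analysis text, not in data collection.

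**Step 4. Can the rows be computed from Section 5.3 alone?** Only in part.

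- Adherence is "Completion of intervention sessions", but no session is defined. Section 11.3 describes a minimum daily viewing time, and Section 11.3.1 describes days and duration of use. The unit could be a participant, a day or a session.
- Section 9.3 allows up to 15 family members in addition to the 25 patients. Section 9.1 lets them use the intervention, and the assessment table gives them several of the measures. Whether they enter any denominator is not stated.
- Section 13.4 analyses all evaluable participants without defining the term.
- For the number recruited, exactly 12 falls in both amber (6-12) and green (12-25).

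**Step 5. Sample size.** The figure of up to 25 is described as pragmatic. No power or precision calculation lies behind it, so there is no figure to reproduce.

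**Step 6. Illustration of precision.** Assumption: the participant is the unit and the denominator is n. The exact (Clopper-Pearson) 95% interval for x out of n runs from the 2.5% point of Beta(x, n − x + 1) to the 97.5% point of Beta(x + 1, n − x).

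| n | Cut-off | Smallest count reaching it | Observed | Exact 95% CI |
|---|---|---|---|---|
| 25 | 80% | 0.80 × 25 = 20 | 80% | 59.3% to 93.2% |
| 25 | 70% (follow-up measures) | 0.70 × 25 = 17.5, so 18 | 72% | 50.6% to 87.9% |
| 12 | 80% | 0.80 × 12 = 9.6, so 10 | 83% | 51.6% to 97.9% |

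A result that only just reaches green has an interval covering much of amber (50-79%, or 50-69% for follow-up measures). If the true rate were 70%, the chance of at least 20 out of 25 is 0.19. These figures describe a study of this size. They would be the same if Section 13 were worded correctly.

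**The case against.** The strongest defence is that the protocol uses the word analysis loosely. Section 14.2 says the questionnaire data will not be analysed and then has them tabulated, so simple tabulation evidently does not count as analysis in the authors' usage. Section 15 excludes only formal statistical analysis. On this reading Section 5.3 is itself the analysis plan: compute the percentage and read off the colour. That is probably what was intended, and it stands as an account of intent. It does not remove the contradiction, because the wording of Sections 13.1, 13.3 and 14.1 is unqualified and Section 5.3 leaves the denominators open.

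A reader might infer that the study, as written, can produce no primary result. The documents do not support that. Section 5.3 commits to assessing every measure, the inputs are collected, and counts and percentages need no separate SAP. The primary objective also includes acceptability, which the interviews address.

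A reader might also take the wide intervals as the size of the error. They are not. They reflect the small sample, and a call made on the point estimate leaves the 0.19 unchanged. Reporting intervals is good practice and separate from the contradiction.

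On monitoring, a reader might infer that the decision against site visits has lost its basis. It has not: low risk is a separate stated reason, Section 21.1 keeps some monitoring of study progress, screening logs go to the trials unit every two months (Section 9.2), and paper forms are checked for missing and out-of-range values (Section 15.2.1). Only the premise about quantitative data is wrong.

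**Conclusion.** The contradiction holds. Three sections exclude the quantitative evaluation that the primary outcome requires, and no analysis section supplies a method for the seven criteria. Since Section 13.3 says no SAP will be generated, this cannot be treated as detail deferred elsewhere.

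The consequence is limited: a primary evaluation whose computation and reporting are not fixed in advance, and an incorrect premise in Section 21.1. It should be fixed, but it does not undermine the study, because the cut-offs are already set and the data are planned. That the authors meant only to exclude formal testing is an inference from Section 15. The precision figures assume participant-level proportions with n of 12 or 25, and they support reporting intervals without adding to the error.

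**What to change.** 1. In Sections 13.1, 13.3 and 14.1, replace the blanket exclusion with a statement that no formal hypothesis testing will be done.
2. Add to Section 14.2, keeping the existing tabulation and mixed-methods triangulation: *Each Section 5.3 criterion will be reported as numerator, denominator and percentage (or count), with an exact 95% CI for participant-level proportions, against the red/amber/green cut-offs. The call uses the point estimate, and a green whose interval extends into amber is reported as such.*
3. State the denominator for each row, including whether family members count and whether adherence is assessed per participant or per session. Define evaluable in Section 13.4, and assign exactly 12 recruits to one band.
4. In Section 21.1, correct the statement that quantitative data collection is lacking, and have the promised monitoring plan cover the screening-log, headset and completeness data.

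The cost is about a paragraph of protocol wording, a few decisions on definitions and one short table in the report. No additional data or participants are needed.
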